## 8.3 Statistical Methods

### 8.3.1 General Principle

Using SAS 9.13 for statistical analysis. All statistical tests should be two-sided. If p-value is less or equal to 0.05, then it is considered to be statistically significant.

Variables data are described by mean±standard deviation, median, maximum and minimum. Use paired t-test to compare intra-group variations with respect to baseline and use ANOVA or Wilcoxon rank-sum test to compare variations between groups.

Attributes data are described as frequency (percentage). Between group comparison of percentages is tested by Fisher's exact test

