#### 4.8 Procedure Table

	Preoperative	Intraoperative	Postoperative	Hospital Discharge	Long-term Follow-up
Eligible criterion and Grouping					
Inclusion, exclusion criteria review	X				
Informed Consent Acquisition	X				
Record demographic information, contact info, diagnosis, type of surgery, cesarean section indication, birth history, preoperative blood loss, comorbidities (past history), blood group ABO, and other abnormalities		X			
Randomization (Dynamic Randomized)			X		
Blood Transfusion					
Intraoperative blood transfusion and other blood products		X	X		
Intraoperative autologous blood transfusion, and related data		X			
Maternal					
Intraoperative anesthesia operation time, special circumstances (such as hypotension), urine output		X			

Intraoperative and postoperative daily bleeding and transfusion, infusion volume (crystal, gel), blood-related drugs		X	X		
The highest body temperature, Hb / Hct / Plt, PT / APTT, ALT / AST / total G / D and renal function (creatinine and urea)	X	X	X		
Postoperative bleeding (drainage, bleeding, lochia, etc.)			X		
Specific causes of postoperative bleeding (uterine inertia, placental conditions, soft birth canal laceration situation)			X		
Test of blood component in recover blood and maternal blood fetal		X (Specimen only)	X (Specimen only)		
Transfusion reaction		X	X		
Other hospitalization					
Time to first mobilisation			X		
Duration of hospital stay				X	
Intraoperative and postoperative adverse events		X	X		
Reoperation caused by bleeding			X		
Inpatient mortality				X	
Overall medical expenses				X	
Tracking for hemolytic disease in future birth					X

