### 2. Sample Size Estimation Based On Population Mean

$$n = \left(\frac{t_{\alpha/2} s}{\delta}\right)^2$$

If  $t_{0.05}=1.96$ ,  $S=709$ ,  $\delta=200$ , the estimated minimum sample size is 50.

3. Thus, according to ratio 1:1, the sample size of IOCS group is also 50.

4. Taking into account the unpredictable factors in the experiment that cause the loss of sample size, we recommend to use 1.2 times the minimum sample size as the sample minimum sample size. Therefore, according to ratio 1:1 between treatment group and control group, the total sample size would be 120 (where 60 for treatment group, and 60 for control group).

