### 8.2.2 Secondary Outcomes

- PT/APTT, Hct and Hb in first and fifth day after surgery
- the number of units of donor blood transfused
- mean fall in serum haemoglobin level
- maternal morbidity resulting from postoperative anaemia
- time to first mobilisation,
- duration of hospital stay
- immediate multidimensional fatigue inventory.
- Total cost in hospital

Second Stage: Follow-up when pregnancy again:

Neonatal hemolytic disease (Appendix 2)

Determine blood type, antibody, and IgG titer)

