### 8.3.2 Significance Level

Use superiority test to compare the primary objective between groups. The significance level  $\alpha= 0.05$  (two-sided).

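### Laboratory outcomes are compared between arms without the preoperative value as a covariate: unbiased, but less precise than the collected data allow

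*Combined protocol and SAP*

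**What the plan says.** Section 8.3.1 (General Principle) is the only general rule for continuous variables. It reads "Use paired t-test to compare intra-group variations with respect to baseline and use ANOVA or Wilcoxon rank-sum test to compare variations between groups". The same section adds "All statistical tests should be two-sided", and counts p of 0.05 or less as significant. Section 8.3 defines neither baseline nor variations.

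The rule reaches these outcomes:

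- Hb and Hct on days 1 and 5, named as primary in section 8.2.1 and listed again as secondary in section 8.2.2.
- PT and APTT on days 1 and 5 (section 8.2.2).
- "mean fall in serum haemoglobin level" (section 8.2.2), given without time points.

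The row of the section 4.8 procedure table that begins "The highest body temperature, Hb / Hct / Plt, PT / APTT" is marked for the preoperative, intraoperative and postoperative columns. Section 3.1.2 also uses preoperative Hb, PT/APTT and platelets to decide eligibility. Sections 4.3 and 4.4 place randomisation after eligibility and consent, and section 4.4 places it during the operation.

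No section names ANCOVA, a baseline covariate or any other adjusted model for a laboratory value. The only regression in the plan is the Cox model for blood loss in section 8.3.3, and it lists no covariates.

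**The concern.** A preoperative measurement taken before allocation is a legitimate covariate and usually the most useful one. This plan collects it and then either subtracts it or ignores it, depending on how section 8.3.1 is read. Subtraction fixes the slope of the postoperative value on the preoperative value at 1, and ignoring baseline fixes it at 0. ANCOVA estimates the slope from the data. Between the preoperative sample and day 1 or day 5 each woman bleeds and is transfused toward a common Hb target (section 4.7), so a slope of 1 has no particular claim here.

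At stake are wider confidence intervals than necessary for Hb and Hct, and for PT and APTT. The last two matter because sections 1.1 and 1.3.1 raise abnormal coagulation after salvage as a safety question.

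The within-arm paired t-tests are a lesser issue. Both arms bleed and are transfused, so each can show a significant change with no difference between them. Such a p-value does not compare the randomised arms.

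**Working it through.** **Inputs.** From section 8.1.1: SD 709 ml, margin 200 ml, multiplier 1.96, minimum 50 per arm, inflation 1.2. Not in the documents: the correlation r between preoperative and postoperative values, and the laboratory SDs. I assume r from 0.1 to 0.7, and a ratio k = SD_pre/SD_post of 0.7, 1 or 1.3.

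**1. The plan's own figure.** (1.96 × 709 / 200)² = 48.3, which rounds up to 49; iterating with t quantiles gives 51. The plan states that "the estimated minimum sample size is 50", so it reproduces within two women. Then 50 × 1.2 = 60 per arm, and "the total sample size would be 120 (where 60 for treatment group, and 60 for control group". The calculation rests on blood loss and contains no laboratory SD or baseline correlation, so nothing below changes the 120.

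**2. Equal SDs (k = 1).** In units of the postoperative variance, the between-arm comparison has variance proportional to 1 for the postoperative value alone, 2(1−r) for the change, and 1−r² for ANCOVA. Change divided by ANCOVA is 2(1−r)/(1−r²) = 2/(1+r).

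| r | Change | ANCOVA | Change/ANCOVA | 60(1+r)/2 |
|---|---|---|---|---|
| 0.1 | 1.80 | 0.99 | 1.82 | 33 |
| 0.3 | 1.40 | 0.91 | 1.54 | 39 |
| 0.5 | 1.00 | 0.75 | 1.33 | 45 |
| 0.7 | 0.60 | 0.51 | 1.18 | 51 |

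The last column is the number per arm at which ANCOVA matches a change-score comparison of 60 per arm. A simulation with 60 per arm and 4,000 runs gave ANCOVA/change ratios of 0.64, 0.75 and 0.86 at r = 0.3, 0.5 and 0.7, against (1+r)/2 = 0.65, 0.75 and 0.85.

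**3. Unequal SDs.** ANCOVA/change becomes (1−r²)/(1+k²−2rk).

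| k | r = 0.3 | r = 0.5 | r = 0.7 |
|---|---|---|---|
| 0.7 | 0.85 | 0.95 | 1.00 |
| 1 | 0.65 | 0.75 | 0.85 |
| 1.3 | 0.48 | 0.54 | 0.59 |

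The gain vanishes when the regression slope r/k equals 1. At k = r = 0.7, for example, the change variance is 1 + 0.49 − 0.98 = 0.51 and the ANCOVA variance is 1 − 0.49 = 0.51. A change is noisier than the postoperative value alone when 1+k²−2rk > 1, that is when r < k/2. The familiar threshold of 0.5 is the case k = 1; at k = 0.7 it is 0.35 and at k = 1.3 it is 0.65.

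**4. If the plan compares postoperative values.** The relevant ratio is the ANCOVA column of step 2, whatever k is: 0.99, 0.91, 0.75 and 0.51. These are large-sample figures. Estimating the slope multiplies the ANCOVA variance by about 1 + 1/(N−4) = 1 + 1/116 = 1.01 at N = 120, which uses up the gain at r = 0.1.

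**The case against.** The strongest case against the point is about reading and size. Section 8.3.1 is loosely worded, and comparing variations between groups may mean no more than comparing the groups. Sections 8.2.1 and 8.2.2 list Hb, Hct and PT/APTT as values on given days; only the fall in Hb is plainly a change. Baseline need not be the preoperative value either, since intraoperative samples are also scheduled. The argument that bleeding and transfusion weaken r cuts both ways: a low r makes a change score look poor, but it also makes the covariate nearly worthless against a comparison of postoperative values (a gain of 1% at r = 0.1 and 9% at r = 0.3, before the small cost of estimating the slope). The formulas apply to ANOVA and not to the Wilcoxon test that the plan also allows. All of this stands, and it limits what can be said about size. It does not remove the omission: under either reading the covariate is unused, and in large samples ANCOVA is no less precise than either alternative.

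A reader might infer four stronger things, none of which the documents support.

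- *That the planned comparison is biased or invalid.* With randomised arms, unadjusted changes and unadjusted postoperative values both estimate the treatment difference without bias and keep the type I error.
- *That 60 women per arm are worth only 33 to 51.* That needs the change-score reading, equal SDs and an assumed r. Under k = r = 0.7 nothing is lost.
- *That a within-arm p-value could carry a claim of success.* Section 8.3.2 says "Use superiority test to compare the primary objective between groups", and section 8.3.3 rests superiority on a between-arm test. No success rule uses a within-arm result.
- *That the blood-loss comparison should take the same covariates.* Section 8.3.3 assigns it to log-rank and Cox. The variance ratios above do not apply there, and covariates in a Cox model change the hazard ratio being estimated.

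**Conclusion.** The point holds as a recommendation on efficiency. The plan does not use preoperative Hb, Hct, PT and APTT as covariates, although they are scheduled and precede randomisation. The planned comparison is valid but less precise than it could be.

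The size cannot be taken from the documents. On the change-score reading with equal SDs, the variance is 1.82 to 1.18 times that of ANCOVA for r from 0.1 to 0.7; with unequal SDs the loss may be larger or may vanish. On the postoperative-value reading, the gain from ANCOVA is negligible at r = 0.1, modest at r = 0.3 and about half the variance at r = 0.7. Neither the 120 women nor the section 8.3.3 decision rule is affected.

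**What to change.** In section 8.3.1:

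1. Define baseline as the last preoperative value, and say what variations means.
2. For Hb, Hct, PT and APTT at day 1 and at day 5, fit the postoperative value on arm plus the preoperative value of the same measure. Ideally include the five stratification factors of section 4.4 as well; with six centres that adds 5 + 4 = 9 parameters. Report the adjusted difference with its 95% CI.
3. If PT or APTT is skewed, use a log transform or a rank-based ANCOVA, and state in advance how that choice is made.
4. Let the same model serve for the fall in Hb. Once the preoperative value is in the model, the arm effect on the fall is the arm effect on the postoperative value with its sign reversed. State the time point of the fall.
5. Keep within-arm changes as description, and say that the paired tests are not evidence of a treatment effect.

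The cost is a paragraph of SAP text, written before the data are analysed. It needs no new measurement, visit or participant.

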### 8.3.2 Significance Level

Use superiority test to compare the primary objective between groups. The significance level  $\alpha= 0.05$  (two-sided).

### 8.3.3 Hypothesis Test

Primary objective: The amount of blood lose post operation:

$$H_0: HR = \frac{\lambda_T}{\lambda_C} < 1, \quad H_1: HR = \frac{\lambda_T}{\lambda_C} \geq 1$$

$\alpha = 0.05$  (two-sided).

By Log-Rank test, if p-value is less or equal to 0.05, and the median amount of blood lose in treatment group is less than in control group, then the superiority of the treatment group relative to the control group holds.

Based on the Cox Proportional hazards model, hazard ratios and the 95% confidence interval (CI), if the lower bound of the CI is greater than 1, then the efficacy of the treatment group is better than that of the control group.

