## 1.3 Risk and Benefit of CSCS

### 1.3.1 Risk

As mentioned earlier, cesarean section has been considered a contraindication to the use of intraoperative cell salvage, due to the theoretical risk of amniotic fluid embolism(an extremely serious, but very low (about one in 200) incidence of pregnancy and maternal complications. However, with the update of technology (new filter equipment), this risk is theoretically even lower. After testing the mothers who has been used cell salvage in cesarean section, we found that after the modernization of equipments, those salvaged, purified and returned blood in cesarean section is the same

as the normal maternal blood.

In addition, during autologous blood transfusion, in theory, the contamination of fetal red blood cell may cause fetal hemolysis in another pregnancy, but there is no evidence that autologous blood transfusion can increase future fetal hemolytic disease.

About autologous blood transfusion and coagulation disorders, the general view is that autologous blood transfusion can wash out heparin and other anticoagulant substances, but there are also typical cases report that after autologous blood transfusion, abnormalities in coagulation index may happen. Since coagulation function and a variety of factors are related, in this trial, we will monitor some of the indicators.

The risks of allogeneic blood transfusions include death from transfusion errors, acute transfusion reactions, fatal lung injury, and transfusion infections.

Compared with the allogeneic transfusion group, there exists potential or undetected adverse events to subjects themselves.

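### The first superiority rule in 8.3.3 takes significance from a two-sided log-rank test but direction from the sample medians, so it can declare IOCS superior when the significant difference favours control

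*Combined protocol and SAP*

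**What the plan says.** Section 8.3.1 states "All statistical tests should be two-sided" and sets the threshold: "If p-value is less or equal to 0.05, then it is considered to be statistically significant". Section 8.3.2 adds "Use superiority test to compare the primary objective between groups", again at two-sided 0.05.

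Section 8.3.3 writes the null as HR (treatment over control) below 1 and the alternative as HR of 1 or more. It then gives two decision rules.

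- **Rule 1 (log-rank):** the condition is "if p-value is less or equal to 0.05, and the median amount of blood lose in treatment group is less than in control group". The stated consequence is "then the superiority of the treatment group relative to the control group holds".
- **Rule 2 (Cox):** "if the lower bound of the CI is greater than 1, then the efficacy of the treatment group is better than that of the control".

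Each rule is worded as sufficient on its own. No conjunction or hierarchy links them.

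**The concern.** A two-sided log-rank p-value says only that the two distributions differ. Rule 1 takes the direction from a different statistic, an untested comparison of sample medians. Rule 2 does not have this fault, because its interval carries its own direction.

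On a right-skewed volume the two statistics can disagree. The pilot table in 8.1.1 shows a 25th percentile of 0, median 274, 75th percentile 700, mean 444 and maximum 4347 ml. The log-rank statistic responds to the upper range and the median ignores it. A heavier upper tail under IOCS could supply the significance while a slightly lower IOCS median supplied the direction. The primary conclusion would then be the reverse of what the test found.

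**Working it through.** **Inputs.** Decision rules, sidedness and alpha come from 8.3.1 to 8.3.3, and the control distribution from the pilot table. For the number per arm, the plan's formula gives (1.96 × 709 / 200)² = 48.3, or 50.9 with t on 47 degrees of freedom. The plan says "the estimated minimum sample size is 50", and 50 × 1.2 = 60 per arm.

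**Assumptions.** Section 8.3.3 defines no time axis, event or censoring. I put ml on the time axis and count every woman as an event. HR above 1 then means less blood loss, which agrees with how Rule 2 reads the HR. Every IOCS distribution below is assumed.

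**Worked data set, 60 v 60.** Control values are q(u) at u = (i − 0.5)/60:
- 0 up to the 25th percentile;
- linear from 0 to 274 at the median, then linear to 700 at the 75th percentile;
- above that, 700 + 430 × ln(0.25/(1 − u)).

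IOCS values are control × 0.8 in the lower 60% and × 2 in the top 40%.

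- Medians: IOCS 221, control 277 ml. Means: 788 v 436 ml, so IOCS women lose about 352 ml more on average.
- Log-rank for IOCS: observed 60, expected 72.34, variance 23.66. z = (60 − 72.34)/√23.66 = −2.54, p = 0.011, in the direction of more bleeding.
- Source of the result: losses up to 277 ml contribute +1.89 to observed minus expected, and losses above 277 ml contribute −14.23.
- Rule 1: p ≤ 0.05 and a lower IOCS median, so IOCS is declared superior.
- Rule 2: HR 0.62, 95% CI 0.42 to 0.91. The lower bound is not above 1 and the whole interval favours control.

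**Frequency at 60 per arm.** Rule 1 was simulated with several thousand trials per scenario and several controls built from the pilot quartiles (SD about 490 to 625 ml). A wrong-direction claim is one where Rule 1 declares superiority and the log-rank statistic favours control.

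| Assumed IOCS effect | Wrong-direction superiority claims |
|---|---|
| None (identical arms) | at most about 0.1% (all claims 2.3% to 2.8%) |
| All losses × 1.5 | about 1% |
| Top 25% × 1.5 or × 2 | 1% to 8% |
| Top 40% × 1.5 | about 5%, up to 13% depending on the control tail |
| Top 40% × 2 | about 16% to 25% |
| Top 40% × 2, other women × 0.8 | 24% to 41% |

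**Sensitivity to the tail.** I repeated the doubled top-40% case with the control above (4,000 trials each). It gave 28% with the tail constant at 430 (mean 438, SD 492) and 13% with 800 (mean 531, SD 714, close to the pilot SD of 709). The range edges are therefore approximate.

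**After the change.** If direction comes from the tested statistic, wrong-direction claims are zero by construction. With identical arms, false superiority is 2.66%, against 2.69% under Rule 1 as written.

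**The case against.** **The rates depend on chosen scenarios.** This stands. Harms that shift all losses barely trigger the fault: total superiority claims were 0.5%, 1.4% and 1.9% with all losses × 1.2, × 1.5 and × 2, and 0.2% with 100 or 200 ml added to every loss. A smooth ramp from × 1 at the median to × 1.5 or × 2 at the extreme gave 1.4% and 6.2%. The largest figures need a jump at the 60th percentile, and the very largest also need IOCS to help most women while sharply harming the rest.

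**A reader might infer that the primary test has no error control.** The documents do not support that as a general statement. With identical arms the claim rate is near the nominal 2.5%, and under the uniform harms above it is lower. Rates well above 2.5% appear only when the upper tail worsens and the lower part of the distribution does not.

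**A reader might infer that the protocol expects this harm.** It does not. Section 1.3.1 gives as the general view that anticoagulants are washed out, then notes "there are also typical cases report that after autologous blood transfusion, abnormalities in coagulation index may happen". Neither that section nor 1.1 says salvage worsens heavy bleeding while leaving the median unchanged or lower. That step is inference.

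**The Cox result would expose the conflict.** It would, and the two paragraphs could be meant to be read together. But the text does not say so, and Rule 1 is complete without Rule 2.

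**Replacing the survival methods would remove the rule.** Only if the median clause goes too. A Wilcoxon test, which 8.3.1 allows, with the median clause kept would still take direction from a different statistic.

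**Conclusion.** The fault is real and lies in a primary decision rule: as worded, Rule 1 can return a conclusion opposite to the significant difference it relies on, and the plan does not resolve the resulting conflict with Rule 2. It is not general type I error inflation.

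Its size depends on whether the loss distributions differ mainly in the upper tail. It is about 1% or less for no effect or uniform × 1.5 harm, single figures for moderate tail harm in most settings, and roughly 16% to 25% (13% to 28% across all the control shapes tried) if the top 40% of losses double. These are illustrative ranges, since the documents give no IOCS distribution and the ml time axis is assumed. The wording defect itself needs none of these assumptions.

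**What to change.** In 8.3.3:

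1. Delete the median clause, and report medians descriptively.
2. Keep one governing rule. Declare superiority only if the two-sided 95% CI for a single named primary effect measure excludes no difference in favour of IOCS.
3. Name that measure. If the Cox analysis is kept, it is HR (treatment over control) with a lower bound above 1. If the survival methods are replaced, it is the between-group difference in blood loss from the replacement analysis. The choice matters because a single HR summarises crossing curves poorly.
4. Restate the null as no reduction in loss on that same measure. As printed, equality (HR = 1) sits in the alternative.

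The cost is SAP wording, with no extra data or patients. The small downside is that the sponsor loses a second route to a superiority claim.

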### 8.3.4 Trial Population

#### 8.3.4.1 Distribution of subjects

- Situation of subjects enrolling in the group and the completion of trial: frequency, percentage;
- Description of the proportion of diagnosed cases in each group.

#### 8.3.4.2 Demographic characteristics, disease characteristics and medical history

Statistically describe indicators, compare between groups to assess the equivalence between the groups

- age;
- height, weight;
- related medical history.

## 9 Data and Record Keeping

### 9.1 Confidentiality Plan

Any research-related documents must be filed with the research center and kept by the investigator. Patient-related documents are filed in accordance with the relevant laws of China. All research related documents must be kept for at least 15 years after the study ends. After this time limit expired, investigators must obtain the consent of the Second Affiliated Hospital of Wenzhou Medical University before discarding any documents. All patient-related data, including identification information and all personal medical information, should be treated as confidential documents. Data verification procedures should be based on the most stringent methods of confidentiality. Prior to obtaining the informed

consent, each patient should be provided with the confidentiality of the personal data, the original data verification, inspection, electronic data processing and file transfer procedures. During the trial, Study team members should keep any relevant information and results confidential. It is strictly forbidden to disclose any of these information to anyone not participating in this study. After the completion of the trial, all case report forms shall be filled in, reviewed and signed by the investigators and ombudsmen in accordance with the data management requirements of this study and kept together with the ‘informed consent’.

